5.1.2 Modified Intention-to-Treat (mITT) Populations

Sensitivity analyses of SVR₁₂ as described in Section 10.5, when applicable, will be performed on the ITT population modified to exclude subjects who do not have HCV GT5 or 6 infection or with multiple/mixed genotypes (final HCV genotype as determined in Section 10.8) (mITT-GT), and on the mITT-GT population further modified to exclude subjects who do not achieve SVR₁₂ for reasons other than virologic failure (mITT-GT-VF).

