6.1.2 Study Days

Study Days (Days Relative to the First Dose of Study Drug)

Study days are calculated for each time point relative to the first dose of study drug. Study days are negative values when the time point of interest is prior to the first study drug dose day. Study days are positive values when the time point of interest is after the

first study drug dose day. There is no Study Day 0. Study Day 1 is the day of the first dose of study drug.

Study Drug End Days (Days Relative to the Last Dose of Study Drug)

Study drug end days are calculated for each time point relative to the last dose of study drug. The last day of study drug dosing is defined as Study Drug End Day 0. Days before it have negative study drug end days and days after it have positive study drug end days.

Final Treatment Value

The final treatment value is defined as the last non-missing measurement collected after Study Day 1 and on or before Study Drug End Day 2.

Final Post-Treatment Value

The final post-treatment value for each subject is the last non-missing measurement collected after Study Drug End Day 2 and on or before Study Drug End Day 999.

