10.0 Efficacy Analysis

10.1 General Considerations

General Considerations

All efficacy analyses will be performed on the ITT population, unless otherwise specified. To support the primary analysis, sensitivity analyses will be conducted for it using the mITT-GT and mITT-GT-VF populations.

Missing data will be imputed for analyses of the HCV RNA endpoints of SVR and virologic failure as described in Section 6.3 and for analyses of PROs as described in Section 6.3 and Section 10.9.

Plasma HCV RNA levels will be determined for each sample collected by the central laboratory using the Roche COBAS® AmpliPrep/COBAS® TaqMan® HCV Quantitative Test, v2.0. The lower limit of detection (LLOD) and lower limit of quantification (LLOQ) for this assay (regardless of genotype) are both 15 IU/mL.

HCV RNA results that are detectable but not quantifiable are reported as "< 15 IU/ML HCV RNA DETECTED" and those that are undetectable are reported as "HCV RNA NOT DETECTED" in the database.

The notation "HCV RNA < LLOQ" is used to represent all HCV RNA values < 15 IU/mL, including values reported as "HCV RNA NOT DETECTED" or "< 15 IU/ML HCV RNA DETECTED." HCV RNA \geq LLOQ are all quantifiable values of 15 IU/mL or greater.

Definitions for Efficacy Endpoints

A confirmed quantifiable value during treatment is defined as any two consecutive HCV RNA measurements \geq LLOQ (or 100 IU/mL for **Breakthrough**), either both during treatment or at the final treatment measurement and the next consecutive post-treatment measurement. A confirmed quantifiable post-treatment value is defined as any two consecutive post-treatment HCV RNA measurements \geq LLOQ.

Breakthrough = confirmed HCV RNA \geq 100 IU/mL after HCV RNA < LLOQ during the Treatment Period; or confirmed increase from nadir in HCV RNA (two consecutive HCV RNA measurements > 1 log₁₀ IU/mL above nadir) at any time point during the Treatment Period. A single breakthrough value (\geq 100 IU/mL or > 1 log₁₀ above nadir) followed by lost to follow-up also will be considered a breakthrough (i.e., will not require confirmation).

EOT failure = HCV RNA \geq LLOQ at end of treatment with at least 6 weeks of treatment, where the HCV RNA value must be collected on or after Study Drug Day 36 and study drug duration \geq 36 days.

On-treatment virologic failure = Breakthrough or EOT failure; if a subject meets both definitions of Breakthrough and EOT failure, he or she will be categorized as Breakthrough only.

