SVR₄ = HCV RNA $<$ LLOQ in the SVR₄ window (4 weeks after the last actual dose of study drug) without any confirmed quantifiable (\geq LLOQ) post-treatment value before or during that SVR window.

SVR₁₂ = HCV RNA $<$ LLOQ in the SVR₁₂ window (12 weeks after the last actual dose of study drug) without any confirmed quantifiable (\geq LLOQ) post-treatment value before or during that SVR window.

SVR₂₄ = HCV RNA $<$ LLOQ in the SVR₂₄ window (24 weeks after the last actual dose of study drug) without any confirmed quantifiable (\geq LLOQ) post-treatment value before or during that SVR window.

Relapse₁₂ = confirmed HCV RNA \geq LLOQ between end of treatment and 12 weeks after last actual dose of study drug (up to and including the SVR₁₂ window) for a subject with HCV RNA $<$ LLOQ at Final Treatment Visit who completed treatment, excluding reinfection as described below.

Relapse₂₄ = confirmed HCV RNA \geq LLOQ within the SVR₂₄ window for a subject who achieved SVR₁₂ and has HCV RNA data available in the SVR₂₄ window, excluding reinfection.

Relapse_{overall} = confirmed HCV RNA \geq LLOQ between end of treatment and up to and including the last HCV RNA measurement collected in the Post-Treatment Period for a subject with HCV RNA $<$ LLOQ at Final Treatment Visit who completed treatment, excluding reinfection.

Virologic failure for SVR₁₂ = On-treatment virologic failure or Relapse₁₂.

Only subjects who have at least one post-treatment HCV RNA value will be included in analyses of relapse. For the analysis of relapse, completion of treatment is defined as any subject with study drug duration of 52 days or greater for Arm A, and 77 days or greater for Arm B. If the last available post-treatment value is \geq LLOQ, then the subject will be considered a relapse (i.e., will not require confirmation).

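### SAP 10.1: a treatment completer whose last on-treatment HCV RNA was quantifiable and drawn before Day 36, and who is viremic afterwards, is outside virologic failure unless Breakthrough applies

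*SAP*

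**What the plan says.** SAP 10.1 defines virologic failure for SVR12 as on-treatment virologic failure (Breakthrough or EOT failure) or Relapse12.

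- **EOT failure** is a quantifiable end-of-treatment value "with at least 6 weeks of treatment". It adds that "the HCV RNA value must be collected on or after Study Drug Day 36" and that dosing lasted at least 36 days.
- **Relapse12** is post-treatment viremia in a subject with HCV RNA below "LLOQ at Final Treatment Visit who completed treatment, excluding reinfection as described below". Reinfection carries the same below-LLOQ condition.
- **Completion**, for relapse, depends on dosing alone: "study drug duration of 52 days or greater for Arm A, and 77 days or greater for Arm B".
- **Final treatment value** (SAP 6.1.2) is the "last non-missing measurement collected after Study Day 1 and on or before Study Drug End Day 2". Nothing requires it to come from late in the course.
- **Breakthrough** has no Day 36 condition. Its two values may be "either both during treatment or at the final treatment measurement and the next consecutive post-treatment measurement".

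Reasons for SVR12 non-response are assigned in order: on-treatment failure, reinfection, Relapse12, premature discontinuation, missing SVR12-window data, other. SAP 5.1.2 excludes from mITT-GT-VF every non-responder whose reason is not virologic failure. That population supplies a sensitivity SVR12 rate (SAP 10.5) and resistance Analyses 2 and 3 (SAP 10.8).

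**The concern.** EOT failure has a minimum sampling day. The final treatment value that gates Relapse12 has none. A completer whose last on-treatment sample is early and quantifiable therefore falls between the two: too early for EOT failure, not suppressed enough for relapse.

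The result is inconsistent. Take two subjects with the same full course, the same missing Week 8 sample and the same post-treatment viremia. The one below LLOQ at Week 4 is a virologic failure. The slower responder, still quantifiable at Week 4, is not. The SAP gives no reason for the difference.

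At stake are the two secondary numerators, the additional endpoint of virologic failure through Post-Treatment Week 12 (SAP 10.7), and the mITT-GT-VF analyses. Each omission lowers the virologic failure count and raises the mITT-GT-VF SVR12 rate.

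**Working it through.** **Check of the interval formula.** With z = 1.96, Wilson limits are [p + z²/2n ± z√(p(1−p)/n + z²/4n²)] / (1 + z²/n). SAP 4.3 gives expected limits at a 97% rate of (84.2%, 99.3%) for n = 30 and (88.2%, 99.1%) for n = 50. Averaging Wilson limits over 200,000 simulated binomial samples gives (84.1%, 99.2%) and (88.2%, 99.1%), agreeing within 0.1 point. The classification argument does not depend on these figures.

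**One record through the rules.** Arm A, 56 days of drug, steady decline to 40 IU/mL at Week 4 (Day 28), no later on-treatment sample, viremic at Post-Treatment Weeks 4 and 12.

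1. Breakthrough: no. The subject was never below LLOQ on treatment, and the final on-treatment value is itself the nadir.
2. EOT failure: no. The value was drawn before Day 36.
3. Reinfection and Relapse12: no. The final treatment value is 40, not below 15 IU/mL.
4. Premature discontinuation: no, since 56 ≥ 52.
5. Missing: no, since the SVR12 window has data.
6. Other: yes.

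**Variants, from coding the SAP 10.1 definitions** (viremic after treatment in all rows):

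| On-treatment profile | Result |
|---|---|
| Week 4 = 40, Week 8 visit on Study Drug End Day 3 | Other |
| Week 2 below LLOQ, Week 4 = 40, no later sample | Other |
| Arm B, Week 4 = 40, Weeks 8 and 12 both missing | Other |
| Week 4 = 40, no later sample, no SVR12-window data | Missing |
| Week 4 below LLOQ, Week 8 missing | Relapse12 |
| Week 2 below LLOQ, Week 4 = 150, Week 8 missing | Breakthrough |
| Week 2 = 30, Week 4 = 400, Week 8 missing | Breakthrough |
| Week 4 sample drawn on Day 36 = 40, Week 8 missing | EOT failure |
| Week 8 = 40 | EOT failure |

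**How the state arises.** SAP 4.2 schedules no visit between Weeks 4 and 8. In Arm A, a missed Week 8 sample is enough. So is one drawn more than 2 days after the last dose, because SAP 6.2 assigns it to the post-treatment period. In Arm B, both Week 8 and Week 12 must be missing.

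**Effect of one such subject, with no other failure.** Expected n is from SAP 4.3. For 0/n the upper limit reduces to z²/(n + z²): 3.84/53.84 = 7.1% and 3.84/33.84 = 11.4%.

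| | As written | Counted as virologic failure |
|---|---|---|
| GT6 virologic failure | 0/50 (0 to 7.1%) | 1/50 (0.4 to 10.5%) |
| GT6 mITT-GT-VF SVR12 | 49/49 (92.7 to 100%) | 49/50 (89.5 to 99.6%) |
| GT5 virologic failure | 0/30 (0 to 11.4%) | 1/30 (0.6 to 16.7%) |
| GT5 mITT-GT-VF SVR12 | 29/29 (88.3 to 100%) | 29/30 (83.3 to 99.4%) |

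**Frequency, by assumption only.** Take about 80 − 16 = 64 Arm A subjects. Assume 2 to 10% have no on-treatment sample from Day 36, 5 to 40% of those are quantifiable at their last sample, and 5 to 20% of those are viremic afterwards. The expected count runs from 64 × 0.02 × 0.05 × 0.05 = 0.003 to 64 × 0.10 × 0.40 × 0.20 = 0.5. The chance of at least one runs from 0.3% to 40%.

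**The case against.** **The last-value sentence might seem to close the gap.** When the last post-treatment value is quantifiable, SAP 10.1 says "then the subject will be considered a relapse (i.e., will not require confirmation"). This waives the second, confirming value only. The below-LLOQ condition at the Final Treatment Visit remains, so the gap stays open.

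**Breakthrough catches some of these subjects.** This stands. A reader might infer that every completer with an early quantifiable last value is lost from virologic failure. The documents do not support that. A value of at least 100 IU/mL after one below LLOQ, or more than 1 log10 above nadir, confirmed by the next post-treatment value, is Breakthrough at any day.

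**The primary result and visibility are protected.** This also stands. The subject is an ITT SVR12 non-responder either way. Non-responders are listed by reason (SAP 10.3), exclusions from mITT-GT-VF are listed (SAP 10.5), and SAP 10.8 still sequences the first post-treatment sample of at least 1000 IU/mL. There is no hypothesis test on these endpoints (SAP 10.2). Listings make the case visible but do not correct the rates.

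**Other data may fill the hole.** SAP 6.3 allows a local laboratory value, and Protocol 5.3.1.1 allows HCV RNA testing of archive plasma. Both help when a central result is missing. Neither helps if no sample was taken.

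**Calling the subject an on-treatment failure would be a new error.** This stands. Nothing was observed after Day 28 in the example, and suppression followed by relapse is at least as plausible. The fix has to leave the timing open.

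**Conclusion.** The gap follows from the SAP wording and gives a wrong classification for a narrow group: completers who do not meet Breakthrough, have a quantifiable last on-treatment value from before Day 36, and are viremic after treatment. They are labelled Other, or Missing without SVR12-window data, and are absent from both secondary numerators, virologic failure for SVR12 and mITT-GT-VF.

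The point is minor. One event moves the genotype-level failure rate by 2.0 points in GT6 (1/50) or 3.3 points in GT5 (1/30), assuming the expected enrolment and no other failure. The documents give no frequency, and the 0.003 to 0.5 range rests wholly on the stated assumptions.

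Two stronger readings should be resisted. A reader might infer that the primary efficacy result is biased; it is not. A reader might also treat 3%, the complement of the 97% in SAP 4.3, as a virologic failure rate and predict a number of misclassified failures. The 97% is a hypothetical observed SVR12 rate, so its complement includes dropouts and missing data. Protocol 5.6.1 reports SVR12 of 97 to 98% in 34 GT1, 54 GT2 and 29 GT3 subjects given 8 weeks, with no virologic failures at that time.

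**What to change.** Add to SAP 10.1 a category, virologic failure with timing undetermined, for a subject who meets all of these conditions:

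- completed treatment (at least 52 days in Arm A, 77 in Arm B) and does not meet Breakthrough;
- has no on-treatment HCV RNA value on or after Day 36, and a final treatment value at or above LLOQ;
- has post-treatment HCV RNA at or above LLOQ, confirmed or as the last available value, up to and including the SVR12 window;
- shows no genotype, subtype or clade switch from baseline.

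Include the category in virologic failure for SVR12, and so in mITT-GT-VF, and align the Post-Treatment Week 12 virologic failure endpoint in SAP 10.7. Place it before Missing and Other in the non-response reasons. Report it beside the on-treatment failure and Relapse12 rates, without adding it to the on-treatment failure numerator.

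The EOT failure sentence needs tidying at the same time: six weeks is 42 days, but its conditions use 36, and SAP 6.1.2 does not define Study Drug Day.

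The cost is one extra derivation branch and a virologic failure rate that may be slightly higher. The primary analysis does not change.

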8.0 Statistical Methods and Determination of Sample Size

8.1 Statistical and Analytical Plans

The primary analysis will occur after all subjects have completed the PT Week 12 Visit or prematurely discontinued treatment. The data for the primary analysis will be locked after data cleaning. Data after PT Week 12 will be added to a new version of the database which will be cleaned and locked at the end of the study.

SAS[®] (SAS Institute, Inc., Cary, NC) for the UNIX operating system will be used for all analyses. All confidence intervals will be two-sided with an alpha level of 0.05.

Descriptive statistics will be provided, such as the number of observations (N), mean, and standard deviation (SD) for continuous variables and counts and percentages for discrete variables.

Safety, and demographic analyses will be performed on all subjects who receive at least one dose of study drug.

Efficacy analyses will be performed on the intention-to-treat (ITT) population defined as all enrolled subjects who receive at least one dose of study drug, unless otherwise specified.

Sensitivity analyses of the primary efficacy endpoint, when applicable, will be performed on the intention-to-treat population modified to exclude subjects not of GT5, 6 according to phylogenetic analyses (mITT-GT), and on the mITT-GT population further modified to exclude subjects who did not achieve SVR₁₂ for reasons other than virologic failure (mITT-GT-VF).

No data will be imputed for any efficacy or safety analysis except for analyses of SVR endpoints (HCV RNA data). HCV RNA values will be selected for the analyses of all SVR endpoints (e.g., SVR₄, SVR₁₂, and SVR₂₄) based on defined visit windows. A backward imputation method will be used to impute missing responses for SVR analyses.

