8.2 Determination of Sample Size

It is anticipated that approximately a total of 80 HCV infected patients, (~30 GT5-infected subjects and ~50 GT6-infected subjects) will be enrolled in the study. A minimum of 15 GT5 and 30 GT6 subjects will be enrolled and up to approximately 16 subjects with compensated cirrhosis (regardless of GT) will be enrolled. No formal hypothesis is being tested. If the observed SVR_{12} rate in this study is 97% among 30 GT5 subjects and 50 GT6 subjects, then the half-width of 2-sided 95% normal approximation intervals are 0.061 and 0.047 for the GT5 and GT6 subjects, respectively.

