4.3 Sample Size

In Phase 2 and 3 studies, Study M14-868 and Study M14-172, GT 5 and 6 subjects were enrolled to demonstrate the pangenotypic efficacy of GLE/PIB across GT1-6 for the label

approved treatment duration. The current study, Study M16-126, serves to generate additional efficacy and safety data from GT 5 and 6 subjects in a wider geographic region. Therefore, no formal hypothesis will be tested in this study. The sample size of this study is determined based on operational considerations of enrolling subjects with less common HCV genotypes.

If the observed SVR₁₂ rate in this study is 97% among the expected 30 GT5 and 50 GT6 subjects, then the expected 95% confidence intervals (CIs) for the SVR₁₂ rate using the Wilson's score method¹ are (84.2%, 99.3%) and (88.2%, 99.1%), respectively, based on the Wilson's score CIs calculated for 1000 simulated samples of 30 GT5 and 50 GT6 subjects with an SVR₁₂ rate of 97% using SAS[®]. The Wilson's score method is expected to be used instead of the normal approximation method because the number of SVR₁₂ non-responders is expected to be less than 5 (see Section 10.3).

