6.3 Missing Data Imputation

Missing Data Imputation for SVR

HCV RNA values will be selected for analysis based on the analysis windows defined in Section 6.2.

For analyses of SVR, subjects' missing visit values will have backward imputation applied, if possible. For backward imputation, if the nearest HCV RNA value after the SVR window is unquantifiable or undetectable, then it will be used to impute the HCV RNA value in the SVR window. If a subject is missing an HCV RNA value within the appropriate SVR window after performing backward imputation, then this value will be imputed with an HCV RNA value from a local laboratory if present; otherwise, the HCV RNA value will be missing. Subjects with missing HCV RNA data in the analysis window, after imputations, will be imputed as a failure.

Regardless of the imputation method described above, if a subject starts another treatment for HCV, then all HCV RNA values for this subject measured on or after the start date of the new HCV treatment will be excluded from analyses. The subject will be considered a failure for summaries of viral response at all time points after the start of the new HCV treatment.

Missing Data Imputation for Virologic Failure

If HCV RNA values from the central laboratory are missing but a local laboratory value is present in the appropriate time period, then the local laboratory value will be used to assess post-treatment relapse and on-treatment virologic failure.

Missing Data Imputation for PRO Questionnaires

The handling of missing data for PROs will be as follows. If a respondent answers at least 50% of the items in a multi-item scale of the Short Form 36 Version 2 (SF-36v2) Health Status Survey, the missing items will be imputed with the average score of the answered items in the same scale. In cases where the respondent did not answer at least

50% of the items, the score for that domain will be considered missing. The Mental and Physical Component Summary measures will not be computed if any domain is missing. Missing data handling conventions for scores related to the Work Productivity and Activity Impairment Questionnaire (WPAI) – Hepatitis C are specified in Section 10.9.

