HCV reinfection is defined as confirmed HCV RNA \geq LLOQ after the end of treatment in a subject who had HCV RNA $<$ LLOQ at Final Treatment Visit, along with the post-treatment detection of a different HCV genotype, subtype, or clade compared with baseline, as determined by phylogenetic analysis of the NS3/4A or NS5A, and/or NS5B gene sequences. Reinfection in the case of the same HCV subtype is defined as a clade switch, as indicated by the lack of clustering between the baseline and post-treatment sequences by phylogenetic analysis. If phylogenetic analysis is not possible due to technical difficulties, HCV reinfection may be determined with a confirmed HCV genotype or subtype switch by the Versant HCV Genotype Inno-LiPA Assay v2.0 or Sanger assay.

Post-treatment relapse is defined as described earlier (**Relapse₁₂**, **Relapse₂₄**, **Relapse_{overall}**), and no genotype, subtype, or clade switch compared with baseline as determined by phylogenetic analysis of the NS3/4A or NS5A, and/or NS5B gene sequences. If phylogenetic analysis is not possible due to technical difficulties, the subject will be defined as having a post-treatment relapse unless an HCV genotype or subgenotype switch is confirmed by the Versant HCV Genotype Inno-LiPA Assay v2.0 or Sanger assay.

Reasons for SVR₁₂ Non-Response

Subjects who do not achieve SVR₁₂ (SVR₁₂ non-responders) will be categorized as having:

1. On-treatment virologic failure (see **On-treatment virologic failure** definition);

2. HCV reinfection (see definition described earlier);
3. Relapse₁₂;
4. Prematurely discontinued study drug with no on-treatment virologic failure (defined as any SVR₁₂ non-responder who prematurely discontinued study drug [study drug duration < 52 days for subjects in Arm A, and < 77 days for subjects in Arm B] and did not meet the **On-treatment virologic failure or HCV reinfection** definitions);
5. Missing follow-up data in the SVR₁₂ window (defined as any subject who completed study drug without data in the SVR₁₂ window after applying the imputation rules and not meeting the definitions of [1], [2], [3], or [4]);
6. Other (defined as any SVR₁₂ non-responder not meeting the definitions of [1] – [5]).

Reasons for SVR₂₄ Non-Response

Subjects who do not achieve SVR₂₄ (SVR₂₄ non-responders) will be categorized as having:

1. On-treatment virologic failure (see **On-treatment virologic failure** definition);
2. HCV reinfection;
3. Relapse₁₂;
4. Relapse₂₄;

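### A relapse first seen after Day 126 in a subject with no SVR12-window sample is neither Relapse12 nor Relapse24, so it is labelled missing follow-up and leaves mITT-GT-VF

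*SAP*

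**What the plan says.** - **Windows (SAP 6.2, Table 2).** In days after the last dose, SVR12 runs from Day 57 to Day 126 and SVR24 from Day 127 to Day 210.
- **Relapse12 (SAP 10.1).** Confirmed HCV RNA at or above LLOQ between end of treatment and "12 weeks after last actual dose of study drug (up to and including the SVR₁₂ window"), for treatment completers who were below LLOQ at the Final Treatment Visit, excluding reinfection. Subjects with at least one post-treatment value are in the relapse analyses.
- **Relapse24 (SAP 10.1).** Confirmed HCV RNA at or above "LLOQ within the SVR₂₄ window for a subject who achieved SVR₁₂ and has HCV RNA data available in the SVR₂₄ window, excluding reinfection".
- **Backward imputation for SVR (SAP 6.3).** When the window is empty, "if the nearest HCV RNA value after the SVR window is unquantifiable or undetectable, then it will be used to impute" the window value. Next, a local-laboratory value may be used. A subject still missing is a failure.
- **SVR12 reason 5, missing follow-up (SAP 10.1).** This covers "any subject who completed study drug without data in the SVR₁₂ window after applying the imputation rules", if reasons 1 to 4 do not apply.
- **mITT-GT-VF (SAP 5.1.2).** The mITT-GT population is "further modified to exclude subjects who do not achieve SVR₁₂ for reasons other than virologic failure". Virologic failure for SVR12 means on-treatment failure or Relapse12 (SAP 10.1).
- **Relapse_overall (SAP 10.1).** It has neither the Day 126 limit nor the SVR12 precondition. It feeds a descriptive table (SAP 10.7) and the choice of subjects to sequence (SAP 10.8).

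**The concern.** The two windowed relapse definitions do not join up. Relapse12 closes at Day 126, and Relapse24 opens only for subjects who achieved SVR12. A subject with an empty SVR12 window and a later positive falls between them.

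The later sample is also used unequally. A negative is carried back and makes the subject an SVR12 success inside mITT-GT-VF. A positive is not carried back, and the subject is removed from mITT-GT-VF as a non-virologic failure.

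Relapse12 is a secondary endpoint. mITT-GT-VF is a sensitivity population for the primary endpoint and the population for resistance Analyses 2 and 3. At the planned response rate very few failures are expected in either genotype, so one misplaced relapse can be the whole virologic signal.

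The SAP is also inconsistent with itself. Section 10.8 sequences this subject as a virologic failure through Relapse_overall, yet Analyses 2 and 3 of that section leave the subject out. Reinfection has no Day 126 limit, so a confirmed reinfection on Day 168 gets its own SVR12 reason, while a relapse on that day is labelled missing.

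**Working it through.** **Inputs.** Protocol 8.1: "All confidence intervals will be two-sided with an alpha level of 0.05", so z = 1.960. SAP 4.3: "97% among the expected 30 GT5 and 50 GT6 subjects". Protocol 8.2: "No formal hypothesis is being tested", so only estimates and intervals are at stake. The windows and rules are those of SAP 6.2, 6.3 and 10.1.

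**The plan's own figures.** Half-width = z × √(0.97 × 0.03 / n):
- n = 30: 1.960 × √(0.0291/30) = 0.0610 (Protocol 8.2 gives 0.061).
- n = 50: 1.960 × √(0.0291/50) = 0.0473 (Protocol 8.2 gives 0.047).

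Averaging the Wilson limits over the binomial distribution at 97% gives 84.1–99.2% and 88.2–99.1%. SAP 4.3 gives 84.2–99.3% and 88.2–99.1% by simulation. These agree, and this point does not dispute them.

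**Tracing the rules.** Take a treatment completer, below LLOQ at the Final Treatment Visit and at Post-Treatment Week 4, not reinfected, with no new HCV treatment and no central or local value in Days 57–126. Only the Day 168 result differs. It is the last available value, so a positive needs no confirmation.

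| | Day 168 at or above LLOQ | Day 168 below LLOQ |
|---|---|---|
| Imputed back to SVR12 window | No | Yes |
| SVR12 (ITT) | Failure | Success |
| Relapse12 | No (after Day 126) | No |
| Relapse24 | No (SVR12 not achieved) | No |
| Relapse_overall | Yes | No |
| SVR12 reason | 5, missing follow-up | none needed |
| SVR24 reason | 7, other (data exist in Days 127–210) | none needed |
| In Relapse12 analysis | Yes, as non-relapser | Yes, as non-relapser |
| In mITT-GT-VF | No | Yes |

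The boundary is sharp. With no other value in the window, a first positive on Day 126 is Relapse12. On Day 127 it is missing follow-up.

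**Size if it happens once.** Assume one such subject in the genotype, with everyone else a treatment completer, an SVR12 success and of confirmed genotype. Wilson limits are (p + z²/2n ± z√(p(1−p)/n + z²/4n²)) / (1 + z²/n), with z² = 3.8415.
- 0/30: upper limit 3.8415/33.8415 = 11.4%.
- 1/30: centre (0.0333 + 0.0640)/1.1281 = 0.0863; half-width 1.960 × √(0.001074 + 0.001067)/1.1281 = 0.0804; limits 0.6% to 16.7%.
- 29/29: lower limit 29/32.8415 = 88.3%.

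| | Relapse12 as written | Relapse12 if counted | mITT-GT-VF SVR12 as written | mITT-GT-VF SVR12 if counted |
|---|---|---|---|---|
| GT5, n = 30 | 0/30 (0–11.4%) | 1/30 = 3.3% (0.6–16.7%) | 29/29 (88.3–100%) | 29/30 = 96.7% (83.3–99.4%) |
| GT6, n = 50 | 0/50 (0–7.1%) | 1/50 = 2.0% (0.4–10.5%) | 49/49 (92.7–100%) | 49/50 = 98.0% (89.5–99.6%) |

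ITT SVR12 is 29/30 or 49/50 under both readings.

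**How often.** At 97%, expected failures are 30 × 0.03 = 0.9 (GT5) and 50 × 0.03 = 1.5 (GT6), 2.4 in all. The rate of empty SVR12 windows is not given. Assume it is 2% to 10%, independent of outcome, and that every failure is a relapse that only a Week 12 or later sample would reveal. Then 2.4 × 0.02 = 0.05 to 2.4 × 0.10 = 0.24 such subjects are expected in the study.

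**The case against.** **The relapse is not hidden.** SAP 10.7 tabulates Relapse_overall by window of first relapse with subject numbers. Non-responders are listed by reason, exclusions from mITT-GT-VF are listed (SAP 10.5), and Analysis 4 lists post-baseline variants for subjects with sequence data. This stands, and it limits the harm. It does not correct the secondary endpoint, the reason tables or mITT-GT-VF.

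**Relapse12 is time-bounded for a reason.** A positive on Day 168 does not prove relapse by Day 126. That is fair, and it is a real cost of the fix. But the current rule counts the subject as a non-relapser and removes the subject from the virologic analysis, which the data support less well.

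**The confirmation waiver may already cover the case.** SAP 10.1 says that a subject whose last available post-treatment value is at or above LLOQ is considered a relapse. Its parenthesis confines this to waiving confirmation. It neither extends the Relapse12 window nor lifts the Relapse24 precondition. If more was meant, the SAP still does not say which relapse category applies.

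**Data lock.** SAP 4.4 does not update SVR12 results after the primary lock. A Week 24 sample taken later cannot alter SVR12 status, whether positive or negative. This stands: the problem affects only samples already in the database at the lock.

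**Day 210.** A reader might infer that the same one-way rule distorts Relapse24 for late Week 24 samples. The documents do not clearly support that. SAP 6.3 confines backward imputation to analyses of SVR, and Relapse24 requires data in the SVR24 window, so late negatives and late positives may both drop out. SAP 10.7's general reference to 6.3 leaves room for doubt but does not settle it.

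**Conclusion.** The gap is real and follows from the SAP text. It affects Relapse12, virologic failure through Post-Treatment Week 12, the SVR12 and SVR24 reason tables, and mITT-GT-VF with resistance Analyses 2 and 3. In those outputs the direction is fixed: relapse is understated and virologic SVR12 overstated. One subject moves GT5 Relapse12 from 3.3% to 0% and GT5 mITT-GT-VF SVR12 from 96.7% to 100%.

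A reader might infer that the primary result is inflated. It is not: the positive subject is an ITT SVR12 failure under either rule.

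The conclusion rests on an empty SVR12 window after local-laboratory substitution, completed treatment, a value below LLOQ at the Final Treatment Visit, no reinfection, and a later sample in the database at the primary lock. The SVR24 label of other applies when the positive falls in Days 127–210. The expected number of such subjects is probably well below one, but that depends on an assumed rate of missed visits. This is a definition worth correcting before lock, not a threat to the primary analysis.

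**What to change.** In SAP 10.1, extend Relapse12, and with it virologic failure for SVR12 and SVR12 reason 3, to subjects who meet all of these conditions:

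- completed treatment (at least 52 days in Arm A, 77 days in Arm B) and were below LLOQ at the Final Treatment Visit;
- have no HCV RNA value in the SVR12 window after local-laboratory substitution;
- have a nearest value after the window at or above LLOQ that is confirmed or is the last available value;
- are not reinfections, with values on or after the start of new HCV treatment disregarded.

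State that this uses the data available at the primary lock, the same data used for backward imputation.

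Optionally, for SVR12 responders, let Relapse24 include a confirmed or last-available value at or above LLOQ after Day 210, excluding reinfection, with any HCV RNA value after Day 126 as the condition for the denominator. The confirmation and reinfection conditions must stay, because Protocol 8.1.2.2 reports reinfection separately from relapse.

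The cost is one or two definition sentences and the matching code, with no new data. The relapse rate may be slightly higher and mITT-GT-VF SVR12 slightly lower. A relapse first seen at Week 24 would be assigned to Relapse12 without its onset having been observed, so a table footnote should say so.
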